### *Feasibility and Acceptability*

Feasibility and acceptability are also assessed through a variety of methods across the study period. Screening outcomes are recorded prospectively including recruitment sources and yield, eligibility rates and ineligibility reasons, and rates of enrollment. We also administer a study-developed questionnaire at baseline (prior to randomization) to assess participant expectations, motivations, and experiences when enrolling in the SPRING RCT. Rates of valid assessment completion are also prospectively recorded. Intervention fidelity with respect to delivery, receipt, and enactment [33] is assessed at each intervention contact (see Intervention Content and Schedule section). A final web-based program evaluation assesses acceptability and includes 22 short-answer, ranking, and multiple-choice questions. The evaluation is distributed after the last intervention lesson to intervention participants only and aims to evaluate participants' perceptions regarding their health, usefulness of the intervention components, general satisfaction and acceptability of the intervention, and suggestions for improvement.

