## Study Objectives

The SPRING study's specific aims are to (1) evaluate the effect of SPRING versus control on objectively measured SED (*primary outcome, hypothesized to decrease*), standing (*hypothesized*

*to increase), and steps per day (*hypothesized to increase*); (2) evaluate the feasibility and acceptability of SPRING, including recruitment, retention, outcome assessment rates, intervention fidelity, and program evaluation; and (3) estimate the preliminary effects of SPRING versus control on maternal-fetal health outcomes including composite APOs (hypertensive disorders of pregnancy, gestational diabetes, and preterm birth), maternal blood pressure and glucose, psychosocial outcomes, gestational age at birth, and infant birth anthropometrics.*

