## **Study Design & Methods**

### *Study Design Overview*

In the absence of established SED-reduction interventions or guidelines in pregnant women, a pilot and feasibility RCT among pregnant women with higher risk for SED and APOs was chosen as the first logical step to determine if the intervention could successfully reduce SED by increasing standing and steps per day across pregnancy (SPIRIT [Standard Protocol Items: Recommendations for Intervention Trials] checklist [13]. The SPRING pilot and feasibility trial is registered on ClinicalTrials.gov (NCT05093842).

Potential participants complete baseline assessments and begin the 1-week baseline activity monitoring protocol between 10 weeks 0 days (100 weeks) and 12 weeks 6 days (126 weeks) of gestation. Upon receipt of valid activity monitoring data with a completed time-use diary and clearance to participate from the participant's prenatal care provider, pregnant women are randomized in a 2:1 ratio to either a multicomponent SED-reduction intervention or a usual care control group. Beginning at approximately 14 weeks of gestation, participants randomized to the intervention group begin the active intervention, which lasts through 38 weeks of gestation or until the participant gives birth, whichever occurs first. Participants randomized to the usual care control arm do not receive the intervention but are mailed a Fitbit Luxe after giving birth.

Participants in both groups complete assessments in each trimester and are remunerated US \$40 for completing the first trimester (baseline) assessment between 100 and 126 weeks, US \$50 for completing the second-trimester assessment between 200 and 226 weeks of gestation, and US \$60 for completing the third-trimester assessment between 320 and 346 weeks of gestation. After participants give birth, maternal-fetal outcomes are abstracted from medical records by trained clinical staff.

All research procedures were approved by the University of Pittsburgh Human Research Protection Office (STUDY20110193).

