### *Randomization*

A randomization ratio of 2:1 (2 intervention to 1 control) was chosen to provide more robust data to evaluate the feasibility and acceptability of our intervention and assessment protocols [16]. To help achieve balance over time, blocks of 6 were selected, and 9 blocks of computer-generated, randomly ordered sets were placed sequentially into sealed, numbered envelopes by a blinded study personnel. These envelopes were then provided to the unblinded study personnel (principal investigator and interventionist) and kept in a secure location.

Participant randomization begins with the blinded study coordinator notifying the principal investigator that a participant is eligible and has completed all baseline assessment procedures. The study investigator then opens the next sequential envelope and records the randomization assignment and date in the randomization log. The principal investigator then contacts the participant to inform her regarding her randomization assignment, describe next steps, ensure that the participant comprehends that the intervention and assessment study procedures are separate, and reinforce the importance of continued participation in either group.

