### *Outcome Assessments*

Study outcome assessments are conducted by trained, blinded study personnel and occur via web-based videoconference once per trimester of pregnancy. Any necessary assessment materials are mailed to participants prior to study visits.

SED and physical activity are measured in each trimester. Objective assessment of activity patterns is conducted using a thigh-mounted activPAL3 monitor (PAL Technologies, Glasgow) worn for 24 hours over 8 days. This protocol is the best-practice methodology for field monitoring of SED and standing [17], and we have shown it to be a valid measure of moderate-

to vigorous-intensity physical activity in pregnant women [18]. Participants wear the monitor on the anterior upper thigh for 8 days, with removal only for swimming activities. Concurrently, participants are asked to record periods of work, nonwork, sleep, and nonwear in a diary for accurate data processing. Participants are verbally instructed regarding procedures for correct monitor wear at each virtual assessment visit, including visual verification of correct placement. Detailed written instructions on monitor wear and diary completion are also provided. The activPAL3 24-hour event data are downloaded and cleaned by removing periods of sleep and nonwear; remaining valid wear time is used to calculate average daily durations of time spent in SED (total and in prolonged bouts of at least 30 and 60 minutes), standing, and stepping. Daily frequency of steps and sit-stand transitions are also averaged across days. Lastly, to estimate moderate- to vigorous-intensity physical activity, time with a stepping frequency of at least 75 steps per minute and 100 steps per minute are averaged across valid wear days from daily summary data. Averages are calculated overall and during working times (if applicable). Data are considered valid with at least 5 days of at least 10 hours of waking wear time recorded [19].

Self-reported SED and physical activity are assessed using the Pregnancy Physical Activity Questionnaire [20], with questions regarding proportion of time spent in SED during work and nonworking times added to improve the accuracy of self-reported SED assessment [21].

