the Sitting during Pregnancy Barriers and Outcome Expectations Questionnaire [24], Expected Outcomes and Barriers for Habitual Physical Activity [25], the Multidimensional Scale of Perceived Social Support [26], and Social Support for Exercise [27]. Validated questionnaires assessing possible psychosocial effects of the intervention include the Profile of Mood States [28], the Centers for Epidemiologic Studies Depression Scale (CES-D) [29], the Perceived Stress Scale [30], Health-Related Quality of Life for Nausea and Vomiting during Pregnancy [31], and the Pittsburgh Sleep Quality Index [32].

Adverse events are collected systematically at follow-up assessment visits by blinded study personnel. Details of new or worsening medical conditions, including pregnancy-related adverse events, are recorded and classified regarding severity and relationship. In addition, ongoing assessment of adverse events in the intervention group is conducted by intervention staff. All adverse events are reviewed by the principal investigator and, if needed, the study physician for accuracy, possible relationship to the intervention, and to make any necessary modifications or terminate participation in the intervention.

Pregnancy health and maternal-fetal outcomes are abstracted from the participant's medical record of prenatal visits and labor and delivery notes. Maternal outcomes extracted include gestational weight gain, clinic-measured blood pressures, pregnancy complications including APOs, glucose screening values, and tolerance tests (if available), and labor and delivery details. Fetal outcomes include gestational age at birth, anthropometrics, and complications. All abstractions are reviewed by a second reviewer and discrepancies are resolved. The study's maternal-fetal medicine physician coinvestigator (AH) confirms all APOs and a random sample of healthy pregnancies for accuracy.

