### *Analytic Strategy Aim 2*

For the recruitment feasibility outcomes, we will calculate frequencies of recruitment method use and yields; rates of screening contacts, consent, eligibility, and randomization; reasons for ineligibility; and characteristics of enrolled participants. Benchmarks will be 42 (80%) for retention and 40 (95%) of the retained participants for valid outcome assessments. Intervention fidelity will be calculated based on intervention contacts with an overall average benchmark of 30 (85%) of each intervention contact completed. Quantitative or semiquantitative acceptability and program evaluation data will be summarized descriptively. Open-ended questionnaires will be analyzed using a constant comparison method to identify salient categories, themes, and

patterns via open coding, iterative review and codebook generation, code linking into similar categories, and final integration into themes [54].

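### Does timing the acceptability survey after the last lesson leave out women who stop the intervention early?

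*Combined protocol and SAP*

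**What the plan says.** Program evaluation belongs to the second aim. Study Objectives lists, under feasibility and acceptability, recruitment together with "retention, outcome assessment rates, intervention fidelity, and program evaluation".

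The instrument is described in Feasibility and Acceptability: "A final web-based program evaluation assesses acceptability and includes 22 short-answer, ranking, and multiple-choice questions". Its timing and recipients follow: "The evaluation is distributed after the last intervention lesson to intervention participants only". It covers the women's view of their health, how useful the components were, satisfaction, and what they would improve.

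Three other places bear on who might not finish the lessons:

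- Study Design Overview starts the intervention at about 14 weeks and gives its end as a period "which lasts through 38 weeks of gestation or until the participant gives birth, whichever occurs first".
- Outcome Assessments has adverse events reviewed, among other purposes, "to make any necessary modifications or terminate participation in the intervention".
- Under Randomization, the principal investigator is to "ensure that the participant comprehends that the intervention and assessment study procedures are separate".

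For analysis, Analytic Strategy Aim 2 summarises the quantitative acceptability data descriptively and adds: "Open-ended questionnaires will be analyzed using a constant comparison method to identify salient categories". It sets benchmarks for retention, valid assessments and completed contacts, and none for acceptability. It states no denominator for the survey.

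**The concern.** The survey has a single stated trigger, and nothing else described would collect the same information later. The other questionnaire written for the study is given before randomisation. Data taken at each intervention contact concern safety and fidelity. The trimester visits measure barriers, mood and similar constructs, and they are not a natural back-up for questions about the programme: "Study outcome assessments are conducted by trained, blinded study personnel".

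The protocol also leaves room for women who do not finish. Participation in the intervention can be ended on safety grounds, birth can come before 38 weeks, and a woman who has been told that lessons and assessments are separate could leave the first and keep attending the second. If such women were never sent the survey, the satisfaction figures and the themes from open-ended answers would come from completers. A complaint held only by those who stopped would not appear, and no analysis can restore answers that were not collected.

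The matter carries some weight because Randomization and Sample Size Considerations justify the 2:1 ratio partly by the wish for more feasibility and program evaluation data. At a fixed total and equal SDs, that ratio raises the variance of the between-group difference by a factor of (1 + 2)² / (4 × 2) = 1.125 compared with 1:1. Having paid 12.5% for data from the intervention arm, the trial would want all of it.

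**Working it through.** **The arm size.** Sample Size Considerations gives 28 intervention and 14 control women before attrition, and 20% attrition. Then 28 / 0.80 = 35, and 14 / 0.80 = 17.5, rounded up to 18. The total is 53, which matches the plan. The survey therefore has at most 35 planned recipients, and one woman not asked is 1 / 35 = 2.9%.

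**What the sentence can mean.** Three readings are open:

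1. Each woman is sent the survey after her own last lesson, whenever that falls.
2. All women in the arm are sent it once the lesson period is over.
3. Only women who reach the final scheduled lesson are sent it.

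Only the third excludes anyone, and it needs a condition that the sentence does not contain. The word restricting recipients separates intervention from control. It does not separate finishers from non-finishers.

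**Which reading the rest of the protocol favours.** The intervention runs from about 14 weeks to 38 weeks, a span of 38 − 14 = 24 weeks, or to birth if that is sooner. Women also enter one at a time as their pregnancies reach 10 to 12 weeks. The end of the intervention is therefore already specific to each woman, which fits the first reading best. Birth does not end contact with the study either: control women are sent a device and an activity report after delivery. A web survey can be sent at any time to anyone who accepts contact.

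**What is not visible.** Feasibility and Acceptability points to Intervention Content and Schedule, but no lesson schedule appears under that heading. References 38, 39 and 41 to 45, mostly on behaviour-change theory, are in the reference list and cited nowhere in the available text. This suggests, without proving it, that a table or box of intervention content was lost when the PDF was read. What counts as the last lesson may be defined there.

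**How large the effect could be under the third reading.** The documents give no rate of stopping lessons early and no expected satisfaction, so this is illustration only. Let *q* be the share who stop and are not asked, *c* the satisfied share among completers and *s* the satisfied share among those who stop. The whole-arm figure is *c*(1 − *q*) + *sq*, so a completers-only report overstates it by *q*(*c* − *s*). Assume *c* = 0.90 and full response among those asked.

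| *q* | Women not asked (35*q*) | Whole arm, *s* = 0.50 | Whole arm, *s* = 0 |
|---|---|---|---|
| 0 | 0 | 90% | 90% |
| 0.05 | 1.75 | 88% | 85.5% |
| 0.10 | 3.5 | 86% | 81% |
| 0.20 | 7 | 82% | 72% |
| 0.30 | 10.5 | 78% | 63% |

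The overstatement runs from nothing to 27 percentage points, driven entirely by assumed values. Under the first two readings *q* = 0 by design, and what remains is ordinary survey non-response.

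**The case for a change.** The best case for a change is that it would be cheap. One sentence could direct the existing survey to every woman allocated to the intervention who still accepts contact, sent by intervention staff so that assessors stay blinded, with responders reported out of all women allocated. The documents do not say how women who stop early, or who give birth before 38 weeks, are to be surveyed, and the fidelity benchmark of 85% of contacts shows that incomplete attendance is expected. It is also true that no other instrument described asks about satisfaction or suggestions.

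The silence stands as a fact. The exclusion does not. The fidelity benchmark concerns contacts completed and is not a stopping rate. The reminder that lessons and assessments are separate comes with encouragement to stay in the study in either arm, and that a woman may leave one and keep the other is an inference from it. The route for ending the intervention described under Outcome Assessments is safety review, not dissatisfaction.

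Women who stop are also visible elsewhere. Receipt and enactment are recorded at each contact they attend, barriers and outcome expectations at every visit, and retention and completed contacts have benchmarks. Finally, the proposed sentence would record a procedure that the current wording already permits, and women who have stopped may well not answer, so the gain is doubtful.

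**Conclusion.** The concern does not hold as a flaw in the plan. What is left is a missing operational detail: which lesson triggers the survey for a woman who stops early, and the denominator against which responses are reported. Staff sending a web survey to one arm of about 35 women would probably send it when each woman's lessons end, and the plan already commits to a participant flow diagram and retention counts against which the number of responders can be read.

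The effect on the Aim 2 acceptability results cannot be estimated from the documents. It is zero under the two readings that exclude nobody, and under the third it depends on a stopping rate that is nowhere given. No benchmark or stated decision uses these results, and the primary outcome, the 42 women required and the 53 planned are unaffected.

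This conclusion rests on two assumptions: that the recipient restriction is by arm, as its wording indicates, and that the missing lesson schedule does not limit the survey to women who complete the final scheduled lesson. If it did, the concern would need to be looked at again, still as a minor point on a descriptive outcome.

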### *Intervention*

#### *Intervention Content and Schedule*

SPRING developed behavioral targets informed by the specific patterns of SED, standing, and daily steps that were associated with lower APO risk in our observation cohort of pregnant

women [11]. Specifically, we observed threshold effects whereby engaging in SED for approximately 9.2 hours per day or less, standing for approximately 3.8 hours per day or more, and accumulating approximately 7801 steps per day or more were the activity patterns associated with a significantly lower risk of an APO [11] along with other maternal and fetal health benefits [46-48]. We also considered additional data from our observational research regarding determinants, barriers, attitudes, and outcome expectations related to SED during pregnancy. Findings from these studies suggested that pregnancy-related physical symptoms such as nausea and fatigue along with work-related sitting were the most commonly reported barriers to reducing SED [24]. Using objectively measured SED data, we also found that desk jobs and fewer children aged 5 years or younger in the home emerged as the factors that are most strongly associated with SED during pregnancy [49]. We then used these data to adapt our existing SED-reduction interventions in nonpregnant adults [50-52] to the new population of pregnant women at high risk for SED and APOs.

Thus, with the overall goal of reducing SED to less than 9 hours per day, we set evidence-based behavioral targets for our intervention as follows: (1) increase standing time by 2-3 hours per day with a daily total target of at least 4 hours per day; (2) increase light-intensity movement across the day, achieving at least 7500 steps per day; and (3) increase steps by at least 250 per hour (up to 8 hours per day). To facilitate behavior change toward these standing and step targets in our intervention group, we developed an evidence- and theory-based, multicomponent intervention strategy across 3 levels of the socioecological model [34,35,37,40].

Safety and fidelity of the intervention are assessed at each contact by measuring contraindications [36], delivery (provision of intervention components), receipt (self-report of intervention components working properly), and enactment (self-report of self-monitoring and goal achievement) [33].

#### *Control Group*

Participants assigned to the control group are asked to continue their typical behavior for the duration of their pregnancy and are provided with a general handout regarding recommended physical activity during pregnancy [36] but received no further intervention materials. After delivery, control participants are mailed a report of their objective activity levels that were previously measured during the study assessments and a Fitbit Luxe.

## **Eligibility Criteria**

We recruit participants in their first trimester of pregnancy who are at risk for high levels of SED and who have at least 1 risk factor for APO. These criteria reflect an early gestational age when we can intervene meaningfully across pregnancy and higher SED appropriate for modification (ie, reduction) to reach the levels that we have found to be associated with better pregnancy outcomes [11]. The criteria of having at least 1 risk factor for APO relate to our long-term goal to test whether our intervention can reduce APO risk; therefore, we sought to evaluate feasibility and preliminary effects in this specific population. Lastly, to allow for our exploratory outcome assessment using prenatal records of maternal-fetal outcomes, participants are required to

consent to abstraction either through our affiliation with the University of Pittsburgh Medical Center or through separate medical record release if they are receiving prenatal care elsewhere.

Participants younger than 18 years or older than 45 years are excluded to avoid an inability to provide consent and more complicated pregnancies with advanced age, respectively. Those with preexisting hypertension or diabetes are excluded because existing management of these conditions could affect our study outcomes (eg, prenatal blood pressure and glucose test results). Any other contraindications to exercise during pregnancy or severe mobility limitation are also exclusionary since the intervention asks participants to increase standing and daily steps. We also require participants to receive clearance for participation in the intervention from their prenatal care provider as an additional safety precaution. Lastly, those participating in other interventional research that could confound our study outcomes are excluded to reduce bias or contamination.

### *Inclusion/Exclusion Criteria*

#### *Inclusion criteria*

##### Gestational age:

- Between 10 weeks 0 days and 12 weeks 6 days of gestation

